1.12 Dose Rationale and Risk/Benefits

Proposed dose: IVIG eye drops 4 mg/ml (0.4%) two times a day.

Rationale: Serum eye drops, compounded by diluting serum by 50% in normal saline, are routinely used for treating ocular surface diseases. The amount of IgG in undiluted serum is approximately 10 mg/ml, therefore 50% serum eye drops has approximately 5 mg/ml IgG, and serum eye drops are generally used four times a day. Since, at 50% dilution serum eye drops are effective in treating ocular surface diseases, we have proposed a similar dose of IgG in IVIG eye drops (4 mg/ml). In our in vitro experiments, we have determined 4 mg/ml IVIG to be non-toxic, as this dose, when added to medium of cultured epithelial cells for 24 hours, did not cause an increase in LDH concentration in the supernatant.

Also, it is generally accepted that IVIG should be given at a concentration that is at least 4 times the concentration of IgG at the application site. In ocular surface diseases, we have estimated IgG amount on the ocular surface to be approximately 0.5 mg/ml, therefore the IVIG dose should be at least 2 mg/ml to be effective. Taken together, our proposed dose of IVIG eye drops replicates the clinically in-use dose of IgG in serum tears, is non-toxic in vitro, and above the threshold required to be effective.

Adverse Effects of IVIG Treatment: To date, IVIG has been administered via systemic route only. Mild to moderate adverse reactions to high-dose IVIG therapy might be seen in nearly 30% of patients. Some of the common adverse reactions include fever, headache, chills, nausea, hypotension, and muscle cramps. Temporary cessation of the IVIG infusion, slow infusion, and use of general anti-inflammatory agents can control these events. Switching to SCIG is another viable alternative. Anaphylaxis can occur in IgA-deficient patients and use of low IgA-containing IVIG preparations is recommended in such cases. Other effects include meningeal inflammation and aseptic meningitis due to the release of inflammatory cytokines and neutrophil activation by IgG Abs within IVIG that mimic antineutrophil cytoplasmic Abs; intravascular hemolysis due to the presence of anti-A or anti-B isoagglutinins or less commonly anti-D or anti-K Abs; thromboembolism because of contamination of IVIG with clotting factors and formation of platelet-leukocyte aggregates; and renal complications due to osmotic injury that could be prevented by using non-sugarstabilized IVIG.

Possible contamination of IVIG with infectious agents like viruses and prions always exists. However, viral inactivation steps, caprylation, and nanofiltration aid in the safety profile of IVIG.

2 Study Objectives

The main objective of this study is to establish whether patients with Dry Eye Disease are able to safely tolerate receiving Intravenous Immunoglobulin (IVIG) eye drops two times a day for eight weeks (primary 'safety and tolerability' objective). The exploratory objective is to investigate the preliminary efficacy of the use of IVIG eye drops in treating Dry Eye Disease (exploratory efficacy objective) to estimate the effectiveness of the trial intervention and collecting data to inform the design of a future definitive trial.

3 Study Design

3.1 General Design

This will be a Randomized controlled trial, in which a total of 28 subjects will be enrolled at 1 clinical site. Subjects will be randomly assigned to one of two groups (#1, #2), with 14 subjects per group. One group will be given placebo (Normal saline eye drops) and the other group will be given eye drops containing the study drug (IVIG).

Patients with established Dry Eye Disease will be approached by a member of the research staff to determine if he/ she might be interested in participating in a research study. If the subject is interested, the research staff member will describe the study. If the subject is willing to enter the study, the study will be discussed and the subject will be asked to sign the informed consent form. Consent will be obtained prior to screening to determine eligibility. Screening procedures include documentation of Dry Eye Disease. Eligible subjects will be enrolled in the study.

All enrolled subjects will receive their first dose of test medication (placebo/ study drug) on study Day 1 in the doctor's office, and after completion of the study assessments, will have the topical eye drops dispensed for self-administration. See Section 5.4 *Preparation and Administration of Study Drug* for details.

Subjects will be provided with diaries to record the time of each dose and will also be asked to record any adverse symptoms. In addition, they will be asked to make a note of any missed doses together with the reason for the omission. Subjects will return at 4 weeks for further study assessments,

thereafter at 8 weeks (the last day of treatment), and again at 10 weeks after two weeks of no treatment with study drug for the final study assessments.

There is no primary efficacy endpoint in this study. Instead several exploratory efficacy endpoints will be assessed.

The primary tolerability endpoint is the change in the test substance tolerance between Day 1 (post-dose) and 8 weeks (56 days).

[figure not shown]

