3.2 Tolerability End Point: Test Substance Tolerance (Visual Analogue Scale)

Subjects will assess their tolerance to the administration of the test medication (placebo/ study drug), utilizing a Visual Analog Scale (VAS). The VAS is a horizontal line with verbal descriptors at either end. The VAS ratings will be completed after administration of the test medication on Day 1 (post-dose), week 4 and week 8. Subjects will place a single slash mark across the horizontal line between the end labeled “completely intolerable” (0 mm) and “easily tolerable” (100mm). The VAS rating is as follows:

Please rate the degree of comfort or lack of comfort associated with administering the eye drop by making one slash mark on the line below:

Visual Analogue Scale

On the scale of 0 to 100 seen below, please mark where you would rate your tolerability to administration of the test drug.

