3.5 Safety Endpoints

Safety assessments include Vital Signs, recording of all complications and adverse events, as well as ophthalmic exam findings. All ocular and non-ocular adverse events will be assessed for severity and relationship to the investigational product.

In addition to the primary tolerability endpoint (Section 2.2), the following safety endpoints will be assessed:

- The proportion of screened subjects who are successfully recruited in the study (i.e., recruitment rate)
- The proportion of eligible subjects at Day 56 who successfully complete (i.e., retention rate, (non)compliance or adherence rate) a full eight weeks (i.e., 56 days) of therapy with topical administration two times per day (BID).
- All reported adverse events, classified by frequency, severity, and relatedness, from baseline (Day 1) through the last study visit (Day 70).
- Clinically significant changes in vital signs or ophthalmic examination from baseline.

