4.4.2 Data Collection and Follow-up for Withdrawn Subjects

If a subject withdraws from the study prior to 8 weeks, the subject will be asked to complete the procedures outlined in the 10 week visit as well as the Test Substance Tolerance scale from 8 weeks, as soon as possible. Subjects who voluntarily withdraw from the study between 8 weeks and 10 weeks will be asked to complete procedures outlined in the 10 weeks visit as soon as possible. Subjects who are withdrawn due to adverse events will be followed at least until resolution or stabilization of the adverse event.

If the subject remains in the study for safety evaluation, follow-up visits will be scheduled according to the schedule of visits and procedures found in the synopsis.

5 Study Drug

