6.5.4 Visit 4: Week 8 (\pm 4 days)

Treatment Visit (after any dose for that day)

- Review the subject's diary and record changes in concomitant medication, deviations from drug schedule and adverse events.
- Vital Signs: Blood pressure, Pulse, and Temperature taken while subject is in a sitting position.
- Visual Acuity (Snellen's chart) with eye glasses (if applicable)
- OSDI
- Symptom Intensity Assessment, SGA and CGA
- Test Substance Tolerance (VAS)
- Keratograph Oculus Redness Score
- > Non-invasive Keratography Tear Film Break-up Time (NIK BUT)
- Schirmer I test
- Baseline Ophthalmic Examination (slit lamp examination, VBR)
- Ocular surface wash collection for analysis (Potential biomarkers)
- InflammDry Test for MMP-9 Protein
- Lissamine Dye Corneal and Conjunctival staining
- Intraocular pressure measurement after topical anesthesia to eye
- **Returning of unused study drug/ placebo (by patient to pharmacy)**

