7.2 Statistical Methods

Based on the classification of reasons for conducting pilot studies by Thabane et al, in this pilot study we will assess the following: (i) Process– recruitment rate, retention rate, (non)compliance or adherence rate; and (ii) Scientific– safety (adverse event/SAE rate), tolerability, and efficacy, including reduction in clinical signs and symptoms (OSDI, Corneal staining, Redness etc as detailed in section 3.4) and treatment effect size. We will calculate the observed rate with 95% confidence interval for each rate by treatment group. Other descriptive statistics, including median with interquartile or mean with standard deviation for continuous variables and frequency with percentage for categorical variables will be reported as well. To estimate the preliminary efficacy under the scientific category, one eye (target eye) will be selected at screening visit as follows: (i) if only 1 eye meets inclusion criteria, this eye is used; (ii) if both eyes meet inclusion criteria, the eye with the higher corneal stain score is used; (iii) if both eyes have the same corneal stain score, then the one with the lower Schirmer I score is used; (iv) if both eyes have same scores, the right eye is used. Secondary analyses will be performed for the non-target eye as well. Due to the nature of this feasibility study, any efficacy statistical tests and adjusted analyses will not be conducted. Detailed data validation will examine completeness, existence and accuracy of collected data to assess data quality and identify missing and conflicting data. Statistical analysis will be performed on an intention-to-treat basis i.e., inclusion of all patients randomly assigned, regardless of adherence, actual treatment received, and subsequent withdrawal of treatment and/or deviation from the protocol and per-protocol (i.e., inclusion of those who completed the treatment as planned) and will be reported according to 2010 CONSORT guidelines. All statistical analyses will be completed using SPSS Statistics V.22.0.31

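### The primary tolerability endpoint is a change between two ratings that both follow the assigned drop, so discomfort present from the first dose cancels out

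*Combined protocol and SAP*

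**What the plan says.** Section 2 gives the main objective as establishing "whether patients with Dry Eye Disease are able to safely tolerate receiving Intravenous Immunoglobulin (IVIG) eye drops two times a day for eight weeks". Section 3.1 turns this into one measure: "The primary tolerability endpoint is the change in the test substance tolerance between Day 1 (post-dose) and 8 weeks (56 days".

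Section 3.2 describes the instrument, a 100 mm line on which higher is better, asking how comfortable it was to put in the drop. On timing it says: "The VAS ratings will be completed after administration of the test medication on Day 1 (post-dose), week 4 and week 8". Section 6.5.2 agrees, listing the first rating among the post-dose procedures on Day 1. There is no pre-dose rating, and none would make sense for a question about administering the drop.

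Section 3.3 says there are no secondary endpoints. The VAS level is not among the exploratory endpoints in Section 3.4 or the safety endpoints in Section 3.5. Section 3.5 does list recruitment, retention and adherence, clinically significant changes in vital signs or the eye examination, and "All reported adverse events, classified by frequency, severity, and relatedness, from baseline (Day 1) through the last study visit (Day 70".

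Section 7.2 names tolerability among the outcomes. Its interval estimates are for rates: "We will calculate the observed rate with 95% confidence interval for each rate by treatment group". Continuous variables get a general provision: "Other descriptive statistics, including median with interquartile or mean with standard deviation for continuous variables". It does not say that VAS scores at each visit are covered, and it specifies no comparison of VAS scores between arms.

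**The concern.** The objective is about level: is the drop tolerable over eight weeks? The endpoint is about drift: does the rating move after the first dose? The reference rating already contains the immediate effect of the assigned drop, so stinging or discomfort that is there on Day 1 and stays is subtracted from itself.

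Section 1.7 says IVIG has not previously been applied to the ocular surface as eye drops, so discomfort from the first dose is an open question for this trial. Taken alone, the primary result could read as no change for a drop rated poorly from first dose to last. It could even read as a benefit if an arm starts low and partly adapts while the other stays near the ceiling. The reader would then have to rely on adverse events, retention and adherence, or on VAS levels that the plan does not expressly commit to report.

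**Working it through.** **Inputs.** The endpoint is from Section 3.1, and the scale and rating times are from Section 3.2. The sample size is from Section 7.1: 12 per arm, with 28 recruited to allow for 10% attrition. That recruitment figure reproduces when worked per arm: 12/0.9 = 13.3, rounded up to 14, and 2 × 14 = 28. It is not in dispute. The documents give no VAS mean, SD or correlation.

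**Within a subject.** Change = week 8 score − Day 1 score. At the ends of the scale, 0 − 0 = 0 and 100 − 100 = 0.

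**Between arms.** Let I1, I8, S1 and S8 be the mean scores for IVIG and saline on Day 1 and at week 8. Let D1 = S1 − I1 and D8 = S8 − I8, the number of mm by which IVIG is worse. Then

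(I8 − I1) − (S8 − S1) = (I8 − S8) − (I1 − S1) = D1 − D8.

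If D1 = D8, the contrast is 0 whatever the gap. If D8 < D1, it favours IVIG even while D8 is above 0. This is algebra and needs no assumption about the SD or correlation.

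**Illustrative cases, saline 90 → 90 mm:**

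| IVIG, Day 1 → week 8 | D1 | D8 | Difference in change (D1 − D8) | Week 8 difference, IVIG − saline |
|---|---|---|---|---|
| 20 → 20 | 70 | 70 | 0 | −70 |
| 20 → 40 | 70 | 50 | +20 | −50 |
| 90 → 70 | 0 | 20 | −20 | −20 |

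The third row shows what the change score can do: it detects late worsening.

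A simulation agreed (12 per arm, 20,000 runs; assumed saline mean 85 mm, SD 15 mm, correlation 0.5). With constant discomfort of 0, 20, 40 and 60 mm, the difference in change stayed within 0.1 mm of zero. The week 8 differences were −0.05, −20.1, −40.0 and −60.0 mm.

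**Precision of reporting the level instead.** The 95% half-width for a difference in week 8 means is t(0.975, 2n − 2) × √(2/n) × SD.

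- n = 12 per arm: 2.074 × 0.408 = 0.85 SD.
- n = 14 per arm: 2.056 × 0.378 = 0.78 SD.
- At 12 per arm this is 8.5, 12.7, 16.9 and 21.2 mm for assumed SDs of 10, 15, 20 and 25 mm.

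For the change score, multiply by √(2(1 − ρ)), where ρ is the correlation between the two ratings. At n = 12 this gives 1.00, 0.85, 0.66 and 0.38 SD for ρ = 0.3, 0.5, 0.7 and 0.9. The two are equal at ρ = 0.5, so the level is the less precise measure only above that.

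**Secondary point, for reconciliation only.** Section 3.2 has a dose before each rating, while Section 6.5.4 describes the week 8 visit as "Treatment Visit (after any dose for that day", which leaves open whether a dose must have been taken. Sections 5.4 and 5.8 supply 56 droppers at two a day, or 56/2 = 28 days. Section 5.9.3 retrieves earlier droppers when the new supply is given at week 4, and the visit windows are 4 days either way. A week 4 visit on day 24 covers dosing to day 24 + 28 = 52, leaving 56 − 52 = 4 planned days (8 doses) uncovered. Separately, a week 8 visit on day 60 falls 4 days after day 56. The main point does not depend on this.

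**The case against.** The algebra is not contested; the case on the other side is about how much it matters.

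- **Section 3.2 is headed as the tolerability endpoint and never mentions change**, so the level might be read as included. That is possible, but Section 3.2 describes the instrument, much as Sections 3.4.1 to 3.4.8 do for endpoints that Section 3.4 mostly defines as changes. Section 3.1 is the only sentence that defines the endpoint.
- **Section 7.2's descriptive statistics would naturally cover a 100 mm scale.** This stands in part. The levels may well be tabulated, but they are not named, and the interval is promised only for rates.
- **There is other evidence.** Besides Section 3.5, there are dosing and symptom diaries (Sections 3.1 and 5.5), a post-dose check for adverse effects on Day 1 (Section 6.5.2), and a 0–10 ocular discomfort score with a pre-dose baseline (Sections 3.4.8 and 6.5.2). These reduce the risk that a badly tolerated drop goes unnoticed. They do not measure the comfort of administering the drop: the discomfort score is an exploratory efficacy measure that also reflects the disease.
- **The 100 mm figure is a limit of the scale, not a forecast.** Agreed. Subjects who found the drop intolerable would probably miss doses, report events or withdraw. The study is also descriptive, with no formal sample size calculation.
- **A week 8 level has its own blind spot**, namely early discomfort that fades or that drives withdrawal. This stands, and is why the Day 1 and week 4 scores should be shown beside it.

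**Conclusion.** The concern holds and should be fixed. As defined, the primary endpoint removes any constant difference in tolerability between the drops and can favour the arm that is worse at week 8. It answers whether tolerance drifts over repeated dosing, which is only part of the main objective.

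The cancellation is exact and assumption-free. Its practical size cannot be estimated, because the documents contain no VAS data; the only bound is the 100 mm length of the scale. The precision figures assume equal SDs at both visits, equal arms (Section 5.3 describes simple randomisation, which need not give them) and an adequate t approximation, which would be rough if ratings cluster near the ceiling.

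The gap lies in the endpoint definition and the reporting plan. The data needed to close it are already collected.

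**What to change.** - **Sections 3.1 and 3.2:** make the week 8 VAS score the primary tolerability endpoint, shown with the Day 1 post-dose and week 4 scores. Keep the Day 1 to week 8 change as supportive.
- **Section 7.2:** state that VAS scores are reported by arm, with the IVIG minus saline difference and its 95% confidence interval, in all randomised subjects. Give the number of missing ratings by arm and visit.
- **Early withdrawals:** Section 4.4.2 asks those leaving before week 8 for the week 10 procedures "as well as the Test Substance Tolerance scale from 8 weeks, as soon as possible". Use that rating, flag it because dosing may already have stopped, and add a summary that excludes such ratings. The second summary favours those who stayed on treatment, so it should sit beside the first and not replace it.
- **Reconcile, without bearing on the main point:** Section 3.2 with Section 6.5.4 on whether a dose precedes the rating, and Sections 5.8 and 5.9.3 with the visit windows in Section 6.5.

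The cost is protocol wording and a little extra analysis, with no added visit, procedure or subject. The level is less precise than the change if the two ratings correlate above 0.5, which is a further reason to keep the change in the report.

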3.2 Tolerability End Point: Test Substance Tolerance (Visual Analogue Scale)

Subjects will assess their tolerance to the administration of the test medication (placebo/ study drug), utilizing a Visual Analog Scale (VAS). The VAS is a horizontal line with verbal descriptors at either end. The VAS ratings will be completed after administration of the test medication on Day 1 (post-dose), week 4 and week 8. Subjects will place a single slash mark across the horizontal line between the end labeled “completely intolerable” (0 mm) and “easily tolerable” (100mm). The VAS rating is as follows:

Please rate the degree of comfort or lack of comfort associated with administering the eye drop by making one slash mark on the line below:

Visual Analogue Scale

On the scale of 0 to 100 seen below, please mark where you would rate your tolerability to administration of the test drug.

3.3 Secondary Study Endpoint

There are no secondary endpoints in this study.

3.4 Exploratory Study Endpoints

The exploratory study endpoints will include:

1. The change in the Ocular Surface Disease Index (OSDI) which is a patient’s subjective rating scale
2. Change in tear secretion as measured by Schirmer I test
3. The proportion of eyes achieving complete corneal staining clearance after treatment
4. Change in corneal staining score as measured by Lissamine dye staining

[figure not shown]
5. The change in subjective ocular surface redness score (OR) using the validated bulbar redness (VBR) grading scale
6. Visual acuity change
7. Change in frequency of administration of artificial tears or concomitant eye drops
8. Change in number of corneal filaments (slit-lamp examination)
9. Change in amount of mucoid films (slit-lamp examination)
10. Clinical Global Impression (CGI) of change in symptoms from baseline (physician's rating)
11. Subject Global Assessment (SGA) of overall change from baseline (subject's rating)
12. Change in Non-Invasive Keratograph Tear Break-Up Time (NIK BUT)
13. Change in Keratograph Ocular Bulbar Redness Score
14. Change in MMP-9 Protein Detection
15. Change in amount of Cytokines in ocular surface wash

3.4.1 Exploratory Efficacy End Point: Ocular surface Lissamine Dye staining score

[figure not shown]
Ocular surface staining will be assessed using Lissamine Green Dye for Cornea and Conjunctiva. The scoring pattern is represented below.

Lissamine Green Dye Staining for Cornea and Conjunctiva:

Using 5uL fixed pipette and a 10uL pipette tip 5uL of the Lissamine will be drawn from the Eppendorf vial and after slightly pulling the eye lid of the patient Lissamine dye will be released over the ocular surface of both eyes. Using the slit lamp nasal-bulbar and temporal-bulbar conjunctiva will be graded within 2 minutes for each eye.

Corneal staining will be graded in 5 zones. Each zone will be graded from 0 to 3 based on the density of punctate staining.

3.4.2 Exploratory Efficacy End Point: Ocular Surface Disease Index (OSDI)

The OSDI rating scale has twelve questions in three discrete areas, with responses rated on a five point scale. Subjects will complete this scale on Day 1 prior to first dose (Baseline), week 4, week 8 and week 10. The questions and scoring system are shown below:⁶¹

HAVE YOU EXPERIENCED ANY OF THE FOLLOWING DURING THE LAST WEEK:

	All of the time	Most of the time	Half of the time	Some of the time	None of the time
1. Eyes that are sensitive to light?	4	3	2	1	0
2. Eyes that feel gritty?	4	3	2	1	0
3. Painful or sore eyes?	4	3	2	1	0
4. Blurred Vision?	4	3	2	1	0
5. Poor vision?	4	3	2	1	0

HAVE PROBLEMS WITH YOUR EYES LIMITED YOU IN PERFORMING ANY OF THE FOLLOWING DURING THE LAST WEEK:

	All of the time	Most of the time	Half of the time	Some of the time	None of the time	
6. Reading?	4	3	2	1	0	N/A
7. Driving at night?	4	3	2	1	0	N/A
8. Working with a computer Or bank machine (ATM)?	4	3	2	1	0	N/A
9. Watching TV?	4	3	2	1	0	N/A

HAVE YOUR EYES FELT UNCOMFORTABLE IN ANY OF THE FOLLOWING SITUATIONS DURING THE LAST WEEK:

	All of the time	Most of the time	Half of the time	Some of the time	None of the time	
10. Windy conditions?	4	3	2	1	0	N/A
11. Places or areas with Low humidity (very dry)?	4	3	2	1	0	N/A
12. Areas that are air conditioned?	4	3	2	1	0	N/A

